2.5 Clinical Studies of 3K3A-APC

A Phase 1 study, ZZ-3K3A-001, was conducted in 64 healthy adult volunteers to characterize the safety and PK profile of single ascending and multiple ascending IV doses of 3K3A-APC. Intravenous administration of 3K3A-APC or matching placebo to cohorts of healthy adult volunteers at doses up to 720 μ g/kg single-dose and 540 μ g/kg multiple-dose (every 12 hours for 5 doses) did not result in any serious adverse events, severe adverse events or withdrawal from study due to an adverse event. After review of AEs (moderate headache, nausea and vomiting and mild vertigo) in 1 of the 2 subjects who received a single-dose of 720 μ g/kg of 3K3A-APC, the SRC recommended reducing the dose to 540 μ g/kg in subsequent subjects in the cohort. For that reason, 540 μ g/kg was the highest dose evaluated in the multiple-dose cohorts. In summary, the

evaluated safety measures indicate that 540 μ g/kg is tolerated in single and multiple dosing in healthy volunteers.

The most common adverse events reported were mild or moderate; headache, hypertension, nausea and vomiting were reported in 54%, 8%, 8% and 4% of the 3K3A-APC treated subjects (n=50) respectively. Rates for the same events in placebo subjects (n=14) were 7%, 21%, 7% and 0%, respectively.

The majority of the drug-related AEs were headache; of subjects who received active drug across the four highest doses, headache occurred at least once in 3/10 (30%) subjects receiving 180 μ g/kg, in 8/10 (80%) subjects receiving 360 μ g/kg, in 9/10 (90%) subjects receiving 540 μ g/kg and in 2/2 (100%) subjects receiving 720 μ g/kg. Headache was reported in 1/14 (7%) subjects who received placebo. These data indicate that headache is related to 3K3A-APC exposure and appears to increase in frequency with dose. In no patient did headache lead to interruption of IMP or require treatment other than acetaminophen pain reliever.

Hypertension was reported with the second highest frequency; ten AEs of hypertension assessed as being related to the treatment occurred during the study. Four (4) of these AEs occurred in placebo-treated subjects (21% of all placebo-treated subjects), and 6 of these AEs occurred in 3K3A-APC-treated subjects (8% of all actively treated subjects). No association of hypertension with 3K3A-APC could be ascribed.

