9.4 Adverse Experience Reporting

The adverse event (AE) definitions and reporting procedures provided in this protocol comply with all applicable United States Food and Drug Administration (FDA) regulations and International Conference on Harmonization (ICH) guidelines. The Site Investigator will carefully monitor each subject throughout the study for possible adverse events. All AEs will be documented on CRFs designed specifically for this purpose. It is important to report all AEs, especially those that result in permanent discontinuation of the investigational product being studied, whether serious or non-serious.

AEs should be collected and reported on subjects who receive investigational treatment from signing of the ICF through study Day 7, and should be followed until resolution or a new baseline is established, but no longer than study Day 90. Any AEs that occur prior to informed consent should be included in the subject's medical history. SAEs will be collected and reported on subjects who receive investigational treatment from signing of the ICF through study Day 30, and should be followed until resolution (or resolution with sequelae), but no longer than study Day 90.

Each clinical study site's Principal Investigator and research team are responsible for identifying adverse events and reporting them through the DCC Online Adverse Event Reporting System. Investigators are also responsible for complying with NeuroNEXT CIRB's reporting requirements for all safety reports. Copies of each report and documentation of IRB notification and receipt will be kept in the Investigator's study file.

Headache has been identified as an AE that we would like to further characterize. Therefore, all headaches that start after signing of the ICF should be documented as AEs, and Investigators should also complete the Headache Record CRF. A new AE form and new Headache Record should be completed for each new headache during the first seven days. Headaches that start prior to signing of the ICF and do not worsen should be reported only on the Medical History CRF and the Headache Record CRF should not be completed. If however, a headache begins prior to consent and later worsens it should be reported as an AE and the Headache Record CRF should be completed.

On-line Adverse Event Reporting System

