6. ANALYSIS POPULATIONS

Since the primary objective aims to estimate a maximum tolerated dose, no formal testing will be involved. All analyses to address the key secondary objectives will be conducted at the 0.05 significance level. The analysis population of interest will differ depending on the objectives of any particular analysis.

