- Grade 5 – Death: The AE results in death

The relationship of the AE to the investigational product should be specified by the Site Investigator, using the following definitions:

- Definitely Related: The reaction follows a reasonable temporal sequence from administration of investigational product; Follows a known or expected response pattern to the investigational product; and is confirmed by improvement on stopping or reducing the dosage of the investigational product, and reappearance of the reaction on repeated exposure. (suspected ADR)
- Probably Related: The reaction follows a reasonably temporal sequence from administration of investigational product; Is confirmed by discontinuation of the investigational product or by re-challenge; and cannot be reasonably explained by the known characteristics of the subject's clinical state. (suspected ADR)
- Possibly Related: The reaction follows a reasonably temporal sequence from administration of the investigational product and follows a known response pattern to the suspected investigational product; Reaction could have been produced by the investigational product or could have been produced by the subject's clinical state or by other modes of therapy administered to the subject. (suspected ADR)
- Unlikely to be Related: The reaction has little or no temporal sequence from administration of the investigational product, and/or a more likely alternative etiology exists.
- Unrelated: Concomitant illness, accident, or event with no reasonable association with treatment.

For the purposes of this study, an AE is considered to be treatment-related if the attribution is possible, probable, or definite. All AEs should be followed until resolution or a new baseline is established, but no longer than study Day 90.

Headache has been identified as an AE that we would like to further characterize. Therefore, all headaches that start after signing of the ICF should be documented as AEs, and Investigators should also complete the Headache Record CRF. A new AE form, and new Headache Record should be completed for each new headache during the first seven days. Headaches that start prior to signing of the ICF, and do not worsen, should be reported only on the Medical History CRF and the Headache Record CRF should not be completed. If, however, a headache begins prior to consent and later worsens it should be reported as an AE and the Headache Record CRF should be completed.

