10.8 Safety Analyses

In addition to the determination of an MTD, additional safety assessments will involve a comparison of treatment-related AEs and SAEs across all 3K3A-APC treated subjects (regardless of dose) versus placebo. First, the percentage of subjects who experience any treatment-related AE or SAE in each group will be compared using a Fisher's exact test. If the null hypothesis is rejected, with a greater frequency observed in the 3K3A-APC group, we will conclude that 3K3A-APC was associated with a significantly greater frequency of treatment-related AEs. If the hypothesis is not rejected, we will conclude that the study does not provide sufficient evidence to conclude that 3K3A-APC was associated with a significantly greater frequency of treatment-related AEs. In addition to an overall comparison, this hypothesis will be repeated for the percentage of subjects having at least one treatment-related AE within each MedDRA system organ class (SOC). If there are significant differences between groups within any specific SOC, then additional tests will compare differences across groups for specific MedDRA preferred terms in order to further explore the cause of observed differences.

In addition to the comparison of percentages in the manner described above, the rates of treatment-related AEs in each group will be compared using the following Poisson regression model:

$$\log\left(\frac{Y_i}{T_i}\right) = \beta_0 + \beta_1 x_{1i} + \epsilon_i$$

where

- Y_i represents the number of treatment related SAEs experienced by the i^{th} subject.
- T_i represents the number of days between the date of randomization and the date of last follow-up for the i^{th} subject.
- $x_i = 1$ if i^{th} subject was randomized to one of the 3K3A-APC dose groups, and 0 if the subject was randomized to placebo group
- ϵ_i is random error for the i^{th} subject

To determine if the rate of treatment related SAEs differ across treatment group we will test the following hypothesis:

$$H_0: \beta_1 = 0 \text{ vs. } H_A: \beta_1 \neq 0$$

If the null hypothesis is rejected, the direction of β_1 will indicate the direction of the observed effect. Values of $\beta_1 > 0$ indicate an increased rate of treatment-related AEs associated with the 3K3A-APC group, while values of $\beta_1 < 0$ indicate a decreased rate of treatment-related AEs associated with the 3K3A-APC group.

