Treatment-related SAEs will be analyzed in the same manner described above. Additional safety analyses will assess all treatment-emergent AEs, treatment-emergent SAEs, unanticipated SAEs, treatment-related & unanticipated SAEs, neuroworsening events, DLTs, and deaths in a similar manner. Finally, all safety analyses will be repeated for each pairwise comparison of subjects in each specific 3K3A-APC dose groups versus the placebo group.

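### The Poisson model for adverse-event rates in SAP 10.8 cannot be run as printed and makes no allowance for overdispersion or for an arm with no events

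*SAP*

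**What the plan says.** SAP 10.8 first compares the percentage of subjects with a treatment-related event by Fisher's exact test. It then adds a rate comparison: "the rates of treatment-related AEs in each group will be compared using the following Poisson regression model". The equation has log(Y_i/T_i) on the left and an intercept, a treatment indicator and ε_i on the right. Y_i "represents the number of treatment related SAEs experienced by the" i-th subject, and ε_i "is random error for the" i-th subject. The test is H0: β1 = 0 against a two-sided alternative, and the sign of β1 is then read as a higher or lower rate on drug.

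The section goes on to treat other safety endpoints, among them "neuroworsening events, DLTs, and deaths in a similar manner", and repeats everything for each dose group against placebo. It mentions no dispersion check, scale factor, robust variance or negative binomial alternative, and no rule for an arm without events. It does not say whether β1 is tested by Wald or likelihood ratio. By contrast, SAP 8.2 falls back to Fisher's exact test when expected counts are small.

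Repeat events in one subject are counted separately. SAP 10.1 is explicit for headache: "A new AE form, and new Headache Record should be completed for each new headache during the first seven days". Protocol 9.4 has the same rule.

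**The concern.** There are three separate problems.

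- **The equation.** It models the logarithm of an observed count, which does not exist for a subject with no event. For treatment-related SAEs, DLTs and deaths, that is likely to be most subjects. The error term also has no place in a plain Poisson regression, so a programmer must guess what was meant.
- **The variance.** If the guess is an ordinary Poisson regression with log T_i as offset, the variance is set equal to the mean. Subjects receive up to five infusions and may have the same event more than once, so some subjects may well contribute several events and most none. The standard error would then be too small, and chance differences in either direction would be declared too often.
- **Empty arms.** With no events in one arm the estimate of β1 is infinite and its Wald test is uninformative. This is realistic for rare events and small dose groups.

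Safety is the trial's primary objective, and the section prescribes directional conclusions from β1.

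**Working it through.** **No figure to reproduce.** The documents give no type I error or power for this model, and no expected event rate or dispersion.

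**Inputs from the documents.** There are 22 cohorts with 3 active subjects each, so 66 active. Placebo is 22 within cohorts, or about 115 − 66 = 49 with the extra placebo subjects.

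**Assumptions.** The level is two-sided 5%; the SAP states 0.05 only for other analyses ("All analyses to address the key secondary objectives will be conducted at the 0.05 significance level"). Variance/mean (φ) is taken from 1.0 to 2.5, and mean events per subject from 0.05 to 2.

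**Step 1: the equation.** Y_i = 0 gives log(0/T_i), which is undefined.

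**Step 2: the only dispersion evidence in the documents.** Protocol 2.5 reports related hypertension in Phase 1.

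- Placebo: 4 events in 21% of 14, i.e. 3 subjects, so counts 1, 1, 2. Mean 4/14 = 0.286; variance (6 − 16/14)/13 = 0.374; ratio 1.31.
- Active: "6 of these AEs occurred in 3K3A-APC-treated subjects (8% of all actively treated subjects", i.e. 4 of 50 subjects. Mean 6/50 = 0.12. Counts 1, 1, 2, 2 give variance (10 − 36/50)/49 = 0.189 and ratio 1.58. Counts 1, 1, 1, 3 give (12 − 36/50)/49 = 0.230 and ratio 1.92.

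The range 1.25–1.95 brackets these values.

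**Step 3: large-sample size.** The true size of a nominal 5% Poisson test is 2·[1 − Φ(1.96/√φ)].

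| φ | 1.0 | 1.25 | 1.31 | 1.58 | 1.92 | 1.95 | 2.5 |
|---|---|---|---|---|---|---|---|
| Size | 5.0% | 8.0% | 8.7% | 11.9% | 15.7% | 16.0% | 21.5% |

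**Step 4: simulation under the null.** Counts are negative binomial, 66 vs 49 subjects, equal T_i, φ from 1.25 to 1.95. A Wald test with an empty arm is scored as non-rejection.

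| Mean events per subject | Wald | Likelihood ratio |
|---|---|---|
| 0.3–2 | 7.1–15.8% | 7.5–16.2% |
| 0.12 | 4.8–10.0% | 8.7–16.1% |
| 0.05 | 0.9–2.1% | 10.4–16.5% |

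With true Poisson counts (φ = 1) and means of 0.3–2, the Wald test runs at 4.4–5.3%; at φ = 2.5 it runs at 20.0–21.2%. For once-only events at 5–15% incidence, Wald runs at 0.2–2.1% and likelihood ratio at 3.7–6.7%.

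**Step 5: an empty arm.** Take 8 of 66 on drug with one event each, against 0 of 49.

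- Wald: p = 0.999.
- Likelihood ratio: 2·8·ln(115/66) = 8.9, p = 0.003.
- Fisher's exact test: p = 0.020.

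For Poisson counts at 0.05 events per subject, the chance that an arm of size n is empty is exp(−0.05n): 9% for n = 49, 33% for n = 22, 55% for n = 12.

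**Step 6: after the fix.** At 66 vs 49, φ 1.25–1.95 and means 0.3–2, quasi-Poisson runs at 4.3–5.1% and sandwich variance at 5.1–6.8%. Negative binomial gave 5.5–6.3%, from about 400 runs per setting (simulation error about ±2 points). None of these Wald tests repairs an empty arm. The sandwich version errs the other way: in the Step 5 example its standard error is √[8·(1 − 8/66)]/8 = 0.33, set against an estimate that diverges, so it would look spuriously decisive.

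**The case against.** A reader might infer that these safety tests do run well above 5%. The documents do not support that as a fact about the trial. They give no dispersion for it, and the Phase 1 evidence is one event type, 10 events, in healthy volunteers. Under a pure Poisson process, 4 placebo events fall in 3 or fewer of 14 subjects with probability 1 − (14·13·12·11)/14⁴ = 37%. The active pattern is less likely by chance (about 2%), but it pools single-dose and multiple-dose subjects over a wide dose range, and unequal exposure alone could produce it. Counting each new headache does not show overdispersion either, since Poisson counts allow repeats. All of this stands, so the size must be stated as conditional.

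A reader might also infer that the model can show nothing when one arm is empty. That holds for the Wald test only. The likelihood-ratio test in the example gives p = 0.003, and the SAP names neither test.

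It is also true that Fisher's exact test on subject percentages is already planned beside the rate model, that the primary result is the MTD with no formal testing, and that the error term makes the equal-variance assumption an inference from the model's name. These points lower the stakes. They do not make the equation usable, and they do not supply a variance suited to repeat events.

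**Conclusion.** The point holds in conditional form. What rests on the text alone is that the printed equation is undefined for subjects with no event, that no provision is made for overdispersion or an empty arm, and that the test of β1 is not named.

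The size of the error rests on an assumed dispersion. At a variance/mean ratio of 1.25–1.95, a nominal 5% Poisson test runs at about 7–16% with 66 vs 49 subjects and 0.3–2 events per subject. It is 5% at a ratio of 1.0 and about 21% at 2.5. For rare or once-only events the direction changes: the Wald test is conservative (about 1–2% at 0.05 events per subject) and gives p near 1 with an empty arm. A plain Poisson likelihood-ratio test survives an empty arm but stays inflated when repeat events are overdispersed.

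The consequence is limited to the secondary safety comparisons. Neither dose allocation nor the MTD uses β1.

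**What to change.** In SAP 10.8:

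1. Write the model as log E(Y_i) = log T_i + β0 + β1·x_i and delete the error term. In the same edit, make the definition of Y_i match the event being compared, since it names SAEs where the text concerns AEs. How T_i should be defined is a separate question.
2. Fit it as a negative binomial regression, or as Poisson with sandwich or quasi-Poisson variance, and name the test of β1.
3. For events that can occur at most once per subject, or when an arm has no events, rely on the Fisher's exact test already planned, or on a likelihood-ratio test from the dispersion-adjusted model. Do not use a Wald test there. Do not use an exact Poisson rate test for repeat events, because it assumes the same Poisson variance.

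The cost is SAP wording, a few lines of code and somewhat wider confidence intervals. No data collection changes, and the MTD decision is not affected.

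### SAP 10.8: the Poisson model meant to compare treatment-related AE rates is defined on counts of treatment-related SAEs, so read literally the AE rate is never modelled

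*SAP*

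**What the plan says.** All of this is in SAP 10.8.

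- **Subject-level test, first.** The "percentage of subjects who experience any treatment-related AE or SAE in each group will be compared using a" Fisher's exact test. It is repeated by system organ class, and by preferred term where a class differs.
- **Purpose of the rate model.** "the rates of treatment-related AEs in each group will be compared using the following Poisson regression model".
- **Response.** Y_i "represents the number of treatment related SAEs experienced by the" i-th subject.
- **Exposure.** T_i "represents the number of days between the date of randomization and the date of last follow-up for the" i-th subject.
- **Hypothesis.** "To determine if the rate of treatment related SAEs differ across treatment group we will test the following hypothesis", namely β1 = 0 against β1 ≠ 0.
- **Interpretation.** Positive values of β1 "indicate an increased rate of treatment-related AEs associated with the 3K3A-APC group", and negative values a decreased one.
- **Closing paragraph.** "Treatment-related SAEs will be analyzed in the same manner described above". It continues: "Additional safety analyses will assess all treatment-emergent AEs, treatment-emergent SAEs, unanticipated SAEs" and further event sets, handled similarly. All safety analyses are then repeated for each dose group against placebo.

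Protocol 8.5.1 describes the safety comparisons only in general terms and contains no Poisson model, so it does not settle the matter.

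**The concern.** The question and the conclusion concern AEs, while the data and the test concern SAEs. A programmer who follows the definition of Y_i would fit an SAE model under an AE label. The closing paragraph would then call for the same SAE model again, and no rate model for treatment-related AEs would be fitted.

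This matters for this drug because the known tolerability signal is non-serious. In Phase 1 (protocol 2.5) there were no SAEs, but headache was reported in 54% of 50 active subjects and 7% of 14 placebo subjects. SAP 10.1 asks for a new AE form for every new headache in the first seven days, so repeat events are recorded. A rate model uses those repeats, whereas Fisher's test counts each subject once. With SAEs as the response, non-serious events never enter Y_i, and β1 carries no information about them.

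**Working it through.** **1. The text side by side**

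| Element of SAP 10.8 | Event type named |
|---|---|
| Purpose of the Poisson model | treatment-related AEs |
| Y_i | treatment-related SAEs |
| Hypothesis sentence | treatment-related SAEs |
| Reading of β1 | treatment-related AEs |
| Repeat in the closing paragraph | treatment-related SAEs |

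The repeat makes sense only if the model before it was meant for AEs. The likely slip is therefore in Y_i and the hypothesis sentence.

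**2. Inputs for an illustration of size**

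The SAP gives no power or event rates for this model, so there is no plan figure to reproduce.

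- Arms: 66 treated and 22 placebo are in SAP 9.2. The approximately 115 subjects exceed the planned 88 by 115 − 88 = 27. If all 27 are placebo (an assumption), the placebo arm is 22 + 27 = 49.
- Alpha: 0.05 two-sided, assumed. SAP 6 states 0.05 for the key secondary objectives only.
- Mean treatment-related AEs per subject, placebo vs active: 0.2 vs 0.5, 0.1 vs 0.4 and 0.07 vs 0.54. All are assumptions. The third pair borrows the Phase 1 headache proportions as event means.
- Mean treatment-related SAEs per subject: equal in both arms at 0.02, 0.05 or 0.10, assumed.
- Equal follow-up in both arms, assumed.

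**3. Formulas**

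- Poisson likelihood-ratio test on arm totals y1 and y0, with e1 = (y1 + y0)·n1/(n1 + n0) and e0 = (y1 + y0) − e1: G = 2[y1 ln(y1/e1) + y0 ln(y0/e0)]. Reject if G > 3.84. Totals are Poisson with mean n × m.
- Fisher's test on subjects with at least one event: q = 1 − exp(−m). For example, m = 0.5 gives q = 0.393 and m = 0.2 gives q = 0.181. Power is summed exactly over both binomials.

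**4. Results**

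Y_i as written (SAEs, equal rates) at 66/49: the rejection probability is 4%, 7% and 6% at SAE means 0.02, 0.05 and 0.10. This is about alpha, as it must be.

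Y_i as treatment-related AEs, compared with the Fisher test already planned:

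| Placebo vs active mean | Poisson on AEs, 66/49 | Fisher, 66/49 | Difference | Poisson on AEs, 66/22 | Fisher, 66/22 | Difference |
|---|---|---|---|---|---|---|
| 0.2 vs 0.5 | 79% | 67% | 12 | 55% | 42% | 13 |
| 0.1 vs 0.4 | 91% | 86% | 6 | 72% | 58% | 15 |
| 0.07 vs 0.54 | 99.9% | 99.6% | under 1 | 97% | 93% | 5 |

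Differences are in percentage points, taken before rounding. Within the Poisson model alone, the loss at 66/49 runs from about 79 − 7 = 72 points to about 99.9 − 4 = 96 points.

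**5. Exposure**

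SAP 10.1 collects AEs through Day 7 and SAP 10.2 collects SAEs through Day 30, but follow-up runs to Day 90 (SAP 1). Dividing by T_i as defined can spread a 7-day AE count over up to 90 days (90/7 ≈ 13) and a 30-day SAE count likewise (90/30 = 3). A common factor cancels from the rate ratio. A difference in follow-up between arms does not. With equal 7-day counts and assumed mean follow-up of 90 and 80 days, the arm rates would differ by 90/80 = 1.125 for no reason connected with AEs.

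**The case against.** The intent is recoverable. The lead-in, the reading of β1 and the closing paragraph all point to AEs, so this is probably a copying slip that a careful programmer would query. That stands, and it makes the fix obvious. It does not make the signed text safe to follow, because the two places that define the computation are the two that say SAEs.

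A reader might infer that the trial would report no increase in treatment-related AEs when there is a large one. The documents do not support that.

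- Fisher's test in the same section covers any treatment-related AE. The Phase 1 headache contrast is itself a proportion of subjects, which is what that test compares. Its exact power for 54% vs 7% is 99.5% at 66/22 and above 99.9% at 66/49.
- All treatment-emergent AEs are analysed as well, AEs are listed and summarised by preferred term and dose, and headache has its own form.
- For the Poisson model the SAP words a conclusion only for the case of rejection. For Fisher's test it treats non-rejection as insufficient evidence, not as proof of no increase.

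A reader might also take the loss of 72 to 96 points as the loss of safety information. It is not. It sets power on AE counts against what is simply the type I error rate of the SAE model, and it ignores the other AE comparisons.

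**Conclusion.** The specification is wrong as written. SAP 10.8 would draw a conclusion about treatment-related AE rates from a test of treatment-related SAE rates, and read literally it never models the AE rate. The contradiction rests on the text alone and needs no numerical assumption.

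The consequence is limited to a supporting event-rate analysis and its by-dose repeats. The CRM and the MTD do not use it. What is lost relative to the planned Fisher test is about 12, 6 and under 1 percentage points in the three scenarios at 66/49, and about 13, 15 and 5 at 66/22. These sizes depend on assumed event means, Poisson counts, equal SAE rates, equal follow-up and a two-sided 0.05 level. The 66/49 split is also an assumption. The point deserves correction because it is cheap and these analyses are meant for the final study report and for regulatory submissions or manuscripts. It does not threaten the trial's main conclusions.

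**What to change.** In SAP 10.8:

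1. Define Y_i as the number of treatment-related AEs for subject i.
2. Reword the hypothesis sentence to refer to the rate of treatment-related AEs.
3. Keep the SAE model as the separate repeat in the closing paragraph, with Y_i there defined as treatment-related SAEs.
4. Define T_i by event type, as time to the end of that type's collection window or to last follow-up if earlier: through Day 7 for AEs and through Day 30 for SAEs. Without this step the corrected AE model would divide a count collected through Day 7 by follow-up that may reach Day 90.

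The cost is a few lines of SAP text and matching program specifications. No new data, visits or procedures are needed.
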